## **E. DATA MANAGEMENT METHODS**

### **E.1. Data Collection, Management and Quality Control**

The MediData RAVE electronic data capture (EDC) system will be used to capture data into the clinical database. The use of EDC will allow secure access to the data and provide an electronic audit trail of all data entered. It will allow a standardized method for data collection that minimizes user bias and maintains consistency. The data will be immediately and remotely accessible and can be easily summarized in a variety of real-time reports. Database programming was conducted in accordance with executed agreement with Bioforum Data Masters vendor master services agreement between Albert Einstein College of Medicine and Bioforum CDMC Ltd. Data will be encoded using unique patient identifiers, and not patient names. IDs will be assigned sequentially, in a manner unrelated to name or other easily identifiable information. Data will be entered for both screened and randomized subjects to allow analyses to assess the degree to which randomized subjects may differ from other potential subjects.

## **F. QUALITY CONTROL METHOD**

### **F.1. Data and Safety Monitoring Committee**

An Independent Data Safety Monitoring Committee (IDSMC) will review safety and clinical outcome data including data on adverse events (AEs) and serious adverse events (SAEs) at regular intervals. The IDSMC will be independent of the investigator and will be empowered to

recommend stopping the study due to safety concerns, but not for efficacy or futility. The IDSMC may review blinded, unblinded, or partially unblinded data, but the investigator will remain blinded until the official unblinding of the database. The IDSMC will meet three times throughout the trial to review/approve the protocol, and to monitor patient accrual and safety. The IDSMC will include within its membership a medical monitor as well as a biostatistician.

A charter will also be prepared for the IDSMC outlining the following:

1. The purpose and responsibilities of the IDSMC
2. IDSMC membership and communications
3. Issues of conflict of interest and compensation
4. Scheduling and organization of Meetings
5. Materials and protocol for IDSMC meetings
6. Reporting requirements for the Cannabidiol (CBDV) vs. Placebo in Children with Prader-Willi Syndrome (PWS) to the IDSMC
7. Reports of IDSMC Proceedings for IRBs
8. Assessment of safety

### **G. DATA ANALYSIS PLAN**

Subject will be randomly assigned (1:1) to CBDV or placebo and followed for 12 weeks. Analyses will be based on the intent-to-treat approach in which subjects are analyzed in the group to which they were originally assigned regardless of compliance. The demographic characteristics of all randomized patients will first be summarized using standard descriptive statistics (means, medians, standard deviations, and ranges for continuous variables and frequencies for categorical variables). Our primary analysis will examine CBDV vs. placebo on the ABC-I. Our secondary analyses will investigate changes in measures of repetitive behaviors (RBS-R, CYBOCS), hyperphagia (HQ-CT), sleep quality (ActiGraph activity monitors), rigid behaviors (MERS-R-PWS), problematic behaviors (other ABC subscales) and global improvement (CGI-I, CGI-S, CSQ). Between group differences in these measures obtained at a specific time point (e.g. 12 weeks) will be compared with the two sample t-test or Wilcoxon rank sum test. In addition, the change in outcome measures between baseline and 12 weeks will be compared between treatment groups. Exploratory analyses will first be performed to evaluate whether the magnitude of changes in these variables between the two time points depends on the baseline value. If there is no evidence that change is dependent on baseline, then two sample t- tests will be used to compare the mean change in each variable between treatment groups; otherwise, analysis of covariance models will be fit to the data where the outcome is the level measured at 12 weeks, and the main effects are treatment group and baseline value. Adjustment for any patient characteristics which appear to be imbalanced across treatment groups will be accomplished by including the relevant terms as main effects into the model. To compare longitudinal trends in outcomes between treatment groups, linear fixed effects models will be fit to all repeated measures obtained during follow-up, with main effects for time and treatment group and a time x treatment interaction term; this is a widely used statistical approach in longitudinal studies of psychiatric outcomes. Appropriate data transformations, such as the log transform, will be applied if the data deviate from the normal distribution.

In any clinical trial, some subjects will be lost to follow up but the expected rate is low given that this is only a 12-week trial. The advantage of the mixed modeling approach is that it can handle data which are missing at random and measurement times which are not evenly spaced. Analyses will also be performed to compare the characteristics of patients who were lost to follow-up and those who completed the trial to assess the degree of any selection bias. Although a number of

different outcomes will be analyzed, we will not adjust for multiple testing given the exploratory nature of this study.

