### **Primary Aim**

To compare CBDV vs. placebo on change in irritability from baseline to endpoint using the Aberrant Behavior Checklist-Irritability Subscale (ABC-I).

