## **H. STATISTICAL POWER and SAMPLE SIZE CONSIDERATION**

### **Power Analysis—Sample Size Justification**

Assuming a common standard deviation for data of 8.27 and using a 2-sided hypothesis test at a 0.05  $\alpha$ -level, a total sample size of 32 participants (16 participants per group) will provide 80% power to detect a significant result assuming a true treatment difference of -8.26 points for the ABC-I score in change from baseline to end of treatment between GWP42003-P and placebo. Allowing for a 10% drop-out rate, a minimum of 36 (i.e. 18 per group) participants need to be randomized into the study. Depending on the drop-out rate during the trial, this number may be increased to ensure a minimum of 32 evaluable participants at Week 12. The assumed SD and treatment mean difference are based on a weighted mean and a pooled standard deviation of estimates from Risperidone trials in irritability in ASD.

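### The ABC-I has three planned comparisons and none is named as deciding the primary aim, so the 5% level is not tied to one test

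*Combined protocol and SAP*

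**What the plan says.** The Primary Aim (section A) is "To compare CBDV vs. placebo on change in irritability from baseline to endpoint", measured by the ABC-I. Section H sizes the trial for that quantity, "assuming a true treatment difference of -8.26 points for the ABC-I score in change from baseline to end of treatment", "using a 2-sided hypothesis test at a 0.05" level.

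Section G names the ABC-I as the primary scale but attaches no time point, model or test to it. One paragraph, covering primary and secondary measures together, then plans:

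- **Level.** Group differences at a time point, with week 12 given only as an example, "will be compared with the two sample t-test or Wilcoxon rank sum test". No rule chooses between the two.
- **Change.** "In addition, the change in outcome measures between baseline and 12 weeks will be compared between treatment groups". A two-sample t-test is used if an exploratory look shows no dependence of change on baseline; otherwise an ANCOVA of the week-12 value is fitted. No threshold is set for that look.
- **Trend.** A longitudinal model with time, treatment and their interaction. The deciding term is not named, and the text calls it a fixed-effects model in one place and a mixed model in the next paragraph.
- **Scale.** "Appropriate data transformations, such as the log transform, will be applied if the data deviate from the normal distribution". No trigger is defined.

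The outcome definition in section C.8 likewise sets week-12 group comparisons beside change from baseline. The end of section G declines multiplicity adjustment because the study is exploratory, and refers to a number of different outcomes.

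**The concern.** The target quantity is largely fixed, but the test that decides on it is not. The level test, the change test and the longitudinal model can disagree in a sample of 32, and a reader of the final report could not tell which was meant to carry the 0.05 level. If whichever is significant may be presented as the primary finding, the chance of a false claim exceeds 5%. The multiplicity statement does not help, because it addresses several outcomes rather than several tests of one.

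The transformation rule adds a further undefined choice. Section C.8.1 gives the ABC-I range as 0 to 45, so a log is undefined at a score of 0 unless an offset is added, and none is specified. A log-scale effect would also no longer estimate the difference in points on which section H is based.

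**Working it through.** **1. The plan's own sample size.** Inputs from section H: difference 8.26, SD 8.27, two-sided 0.05, 80% power, 10% drop-out.

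- n per arm = 2 × (1.960 + 0.842)² × (8.27/8.26)² = 15.7, so 16.
- Normal approximation at 16 per arm: 8.26 / (8.27 × √(2/16)) = 2.825; power = Φ(2.825 − 1.960) = 0.806. The exact noncentral t gives 0.780.
- 32 / 0.9 = 35.6, so 36 randomized.

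The figures reproduce for one two-sided t-test of change. The sample-size arithmetic is not at issue.

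**2. False-positive rate when several ABC-I tests can count.** Null simulation: 16 per arm, ABC-I at baseline and weeks 4, 8 and 12, SD 8.27 at each visit, 6,000 trials per setting. Assumptions not in the documents: mean 25; within-patient correlation ρ of 0.3, 0.5 or 0.7; one case with correlation decaying over time. The settings were repeated with baseline restricted to 18 or more and scores held to 0 to 45. The change path follows section G, with p<0.05 for the baseline–change correlation as an assumed trigger for ANCOVA. The longitudinal test is a t-test of per-patient slopes. A trial counts if any listed test has p<0.05. Values in brackets are with the baseline restriction.

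| ρ | Level t-test + change path | + slope, weeks 0–12 | + slope, weeks 4–12 instead |
|---|---|---|---|
| 0.3 | 6.5% (6.2%) | 9.2% (8.8%) | 10.0% (9.8%) |
| 0.5 | 7.2% (7.5%) | 10.1% (9.6%) | 11.2% (11.4%) |
| 0.5, decaying | 8.0% | 10.1% | 11.2% |
| 0.7 | 8.7% (8.6%) | 10.5% (10.2%) | 12.3% (11.9%) |

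Simulation error near 5% is √(0.05 × 0.95 / 6000) = 0.3 percentage points. A separate simulation of the same kind gave 6–9% and 8–11%, hence the rounded ranges of 6–9% and 8–12%.

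**3. Where the excess comes from.** Each test alone holds its level (4.0–5.5%). The two-step change path alone gives 4.9–5.4%. The excess arises from running level, change and trend side by side. It grows with ρ in the first column because the level and baseline-adjusted estimates have correlation √(1 − ρ²), that is 0.95, 0.87 and 0.71 for ρ = 0.3, 0.5 and 0.7: they agree less as ρ rises.

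**4. Worst cases.** Counting the t-test, Wilcoxon, change t-test, ANCOVA, slope and log versions together gives 10.8–13.2%. Counting level, change path, follow-up slope and the average treatment effect over follow-up gives 12.7–14.4%.

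**5. One fixed ANCOVA.** Its simulated level is 4.8–5.5%. If 8.27 is the SD of change and the variances at baseline and week 12 are equal, its residual SD is 8.27 × √((1 + ρ)/2) = 6.67, 7.16 and 7.62 for ρ = 0.3, 0.5 and 0.7. With 16 per arm, a difference of 8.26 and 29 degrees of freedom, noncentral-t power is 92%, 88% and 84%. Simulation gave 83–92%, against about 78% for the change t-test.

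**The case against.** The strongest reply is that the plan is less open than it looks. The Primary Aim and section H agree on change from baseline, section G gives a conditional rule for analysing change, and the longitudinal model is introduced for trends, a different question. On that reading only one sentence is missing, and a single-site pilot that calls itself exploratory may not need more. Much of this stands: the target is largely fixed, and a reader who inferred that the plan has no primary quantity would go too far. But change t-test, ANCOVA and longitudinal model can each claim to address that target, and section C.8 places week-12 levels beside it.

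It can also be said that the level test in section G refers to the secondary measures only. That reading is possible. It removes one test, but leaves the change path and the longitudinal model without a hierarchy.

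Other stronger inferences are not supported:

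- That the error rate is 10% or more in any event. The highest figures count alternatives joined by or and otherwise as if all were run.
- That the data-dependent choice between t-test and ANCOVA inflates the error by itself. It holds about 5%.
- That the power statement is void. It reproduces for the planned change t-test.
- That the −8.26 shows log-transformed changes to be undefined. It is a between-arm difference, not a within-patient change, and section G does not say that the log applies to change scores.
- That the sponsor means to select a favourable result. The plan does not say so; it only fails to rule it out.

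**Conclusion.** The concern holds in a limited form. Change in ABC-I to week 12 is the primary quantity, but no single test is named as deciding it, and the no-adjustment statement does not cover several tests of one outcome. If any significant ABC-I result could be reported as primary, the false-positive rate is about 6–9% for level plus change path and about 8–12% with the slope test, instead of 5%. This rests on that reporting assumption, on 16 evaluable patients per arm, and on assumed correlations of 0.3–0.7. Covariates added for observed imbalance, which section G also allows, were not simulated and could add to it. The excess is moderate, but the choice cannot be made credibly after unblinding.

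**What to change.** In section G, name one primary test: the CBDV–placebo difference in week-12 ABC-I from an ANCOVA with baseline ABC-I always included, two-sided 0.05, on the original point scale. For this outcome:

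- drop the data-dependent choice between t-test and ANCOVA;
- do not apply the transformation rule;
- label the week-12 t-test or Wilcoxon, the change t-test and the longitudinal trend as supportive.

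The cost is wording. The sample size is unchanged, and the only loss is that the other ABC-I analyses can no longer decide the primary aim. By comparison, keeping three co-equal tests with a Bonferroni split (0.05/3 = 0.0167 each) would cut power at 16 per arm to about 62%. Restoring 80% would need 23 per arm: 46 evaluable, and 46/0.9 = 51.1, so 52 randomized in equal arms.

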## **III. CBDV and Irritability in PWS**

Individuals with PWS frequently exhibit irritability, which manifests as a consequence of emotion dysregulation, disruption of rigid behavioral patterns or excessive response to stimuli. Irritability is a well-characterized outcome that has been accepted by the FDA for the purposes of labeling in other cohorts. The FDA has approved treatments for irritability in ASD, including aripiprazole and risperidone, based on the Aberrant Behavior Checklist (ABC) – Irritability subscale.

In animal models of neurodevelopmental disorders, CBDV has been shown to reduce hyperactivity, which may be suggestive of an improvement in irritability.

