### **III. Baseline (visit 1, week 1, in-person)**

At the baseline visit, subject will be re-consented. Repeat drug and pregnancy test (if applicable) will be done. In the case of positive result, testing will be repeated for confirmation. Confirmed positive results will lead to exclusion.

For subjects who continue to meet study criteria, study clinician will review concomitant medications, obtain vital signs, weight, BMI, IQ test, ABC, RBS-R, CY-BOCS, Actigraphy Remote sleep measurement, Caregiver Strain Questionnaire, CGI-S, HQ-CT, MERS-R-PWS and C-SSRS. Body composition will be assessed using bio-impedance analysis. A physical and neurological exam will be performed. ECG will be done. Safety labs including CBC, BMP, LFT, and concomitant plasma drug levels of valproic acid, lamotrigine, oxcarbazepine, phenytoin and clobazam for those patients who take them will be drawn. Dietary diary will be completed by participant and reviewed. Blood sample will be collected and preserved for biorepository for consented patients. Actigraphy data collected prior to in person visit will be reviewed.

For subject that meet all inclusion/exclusion criteria after all assessments, they may enroll and be randomized to a study group at this visit. The study pharmacist at the Clinical Research Pharmacy will use a computer-generated randomization table to randomize subjects in a 1:1 ratio.

Enrolled patients will receive a weight-based dosing up to 10 mg/kg/day of CBDV (max 800 mg/day) or placebo for 12 weeks on a titration schedule as specified in protocol, administered b.i.d with food.

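### Covariates for the primary ABC-I model are chosen by an undefined post-randomisation imbalance rule instead of being fixed in advance for prognostic value

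*Combined protocol and SAP*

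**What the plan says.** Section G makes the between-group comparison on ABC-I the primary analysis. Two features of that model are left to the data.

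- Baseline ABC-I: an exploratory look decides whether it enters. "If there is no evidence that change is dependent on baseline, then two sample t- tests will be used to compare the mean change"; otherwise ANCOVA is fitted to the week-12 score with treatment and baseline as main effects.
- Other characteristics: "Adjustment for any patient characteristics which appear to be imbalanced across treatment groups will be accomplished by including the relevant terms" as main effects. The section does not say which characteristics are screened, how imbalance is judged, how many terms may enter, who decides, or whether the decision precedes unblinding.

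On allocation, the baseline visit description (C.9.2, III) says the pharmacist will "use a computer-generated randomization table to randomize subjects in a 1:1 ratio", with no stratification factor. Section H states that "a total sample size of 32 participants (16 participants per group) will provide 80% power", with no mention of covariates. Section C.1 calls the trial a pilot, and section G calls it exploratory when explaining why it makes no multiplicity adjustment.

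**The concern.** After proper randomisation a baseline difference is a chance event. Whether adjustment helps depends on whether the variable predicts ABC-I, not on whether it differs between arms.

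Selecting on imbalance has three effects:

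- It picks variables because they correlate with treatment in this sample. If they do not predict outcome, the standard error of the treatment effect rises.
- It omits prognostic variables that happen to be balanced, and so gives up precision.
- With no cut-off and no timing, different analysts could reach different primary models from the same data, and nothing stops the choice being made with results in view.

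The evaluable sample size of 16 per arm is the bare minimum from the power formula, so there is little margin for an inefficient model.

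**Working it through.** **The plan's own figure.** Section H gives: "Assuming a common standard deviation for data of 8.27 and using a 2-sided hypothesis test at a 0.05" level; "assuming a true treatment difference of -8.26 points for the ABC-I score in change from baseline to end of treatment"; 80% power.

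- n per arm = 2 × (1.960 + 0.842)² × (8.27/8.26)² = 15.7, rounded up to 16.
- Power at 16 per arm is 80.6% by the normal formula and 78.0% by the noncentral t with 30 df.
- 32/0.9 = 35.6, rounded up to 36, which agrees with "Allowing for a 10% drop-out rate, a minimum of 36 (i.e. 18 per group) participants need to be randomized into the study".

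The plan's figures reproduce.

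**Chance of a flag.** Let SMD be the standardised mean difference. For a continuous variable with no true difference, P(|SMD| > c) = 2 × P(t₃₀ > c × √(16/2)) = 2 × P(t₃₀ > 2.828c). The protocol gives no cut-off, so a range is shown.

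| Assumed cut-off | Flagged by chance |
|---|---|
| SMD > 0.1 | 78% |
| SMD > 0.2 | 58% |
| SMD > 0.25 | 48% |
| SMD > 0.5 | 17% |
| p < 0.10 | 10% |
| p < 0.05 | 5% |

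At the 18 per arm randomised, SMD > 0.25 gives 46%, so the choice between 16 and 18 matters little.

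**Power with baseline ABC-I in the model.** Assumptions not in the protocol: correlation 0.5 between baseline and the analysed outcome (residual SD = 8.27 × √0.75 = 7.16), and 8 or 12 independent, non-prognostic candidates. Simulated ANCOVA, 16 per arm, difference 8.26, two-sided 0.05. Ranges are from repeat runs of 4,000 to 8,000 trials. With baseline only, power is about 87%.

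| Cut-off | 8 screened: terms added, power | 12 screened: terms added, power |
|---|---|---|
| SMD > 0.25 | 3.9, 77–78% | 5.8, 71–73% |
| SMD > 0.5 | 1.3, 81–82% | 2.0, 78% |
| p < 0.10 | 0.8, 82–83% | 1.2, 81% |
| p < 0.05 | 0.4, 83–84% | 0.6, 83% |

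The loss is therefore about 3 to 16 points (87 − 84 to 87 − 71). The very loose cut-off SMD > 0.1 goes lower, to 75% and 67%. At SMD > 0.25 with 8 screened, the standard error rises by about 14%.

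**Power without baseline adjustment (reference 78.0%).**

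- Non-prognostic candidates, SMD > 0.25: 70.5% with 5 screened, 63.9% with 10.
- Non-prognostic candidates, p < 0.05: 76.7% with 5 screened, 74.3% with 10.
- Candidates jointly explaining 30% of outcome variance, SMD > 0.25: 79.5% with 5 screened (no loss), 71.3% with 10. Fitting all 5 regardless of balance gives 83.6%.

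**Type I error.** Applied mechanically, the rule gave about 4.5% to 5.4% with non-prognostic candidates. With prognostic ones at SMD > 0.25 it was conservative, at 3.4% to 3.8%. If the smaller of the adjusted and unadjusted p-values is reported, the error is 7% to 8% at SMD > 0.25 and about 6% at p < 0.05 with 8 screened.

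**Fixed covariates, 16 per arm.**

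- One covariate: 76.7%, 80.6% and 87.3% for correlations of 0, 0.3 and 0.5.
- Three covariates, only the first prognostic: 73.2%, 77.5% and 84.8%.

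A useless extra covariate costs (76.7 − 73.2)/2 = 1.75 points at correlation 0 and (87.3 − 84.8)/2 = 1.25 at 0.5.

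**The case against.** The strongest reply is that the damage depends on details the protocol leaves unstated. Read as a significance test, the rule flags only 5% to 10% of variables and costs a few points of power. Several of the simulated settings stay at or above the planned 80%, because the 87% starting point already includes an assumed gain from baseline adjustment. If the screened variables predict outcome, the loss can disappear. Section G puts the baseline summary first, and section F.1 keeps the investigator blinded until the database is officially unblinded, so covariates could be settled before results are seen. The study is a pilot.

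Most of this stands, and it bounds the size of the point. It does not rescue the criterion: in the case with five prognostic candidates, fixed adjustment still gave 83.6% against 79.5% under the rule. Nor do F.1 and the order of steps in G require that covariates be settled before outcomes are compared. The exploratory label is used in G to justify no multiplicity adjustment across outcomes; G still names a primary analysis, and H powers it.

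Stronger readings that the documents do not support:

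- **About half of all variables will be flagged.** This needs a cut-off near SMD 0.2 to 0.25, which the protocol does not state.
- **The rule inflates type I error.** Used as written, it does not. Inflation needs selective reporting, which the text neither plans nor prevents.
- **The rule removes the planned power.** This holds only for many non-prognostic candidates combined with a loose cut-off.
- **Antipsychotic use must be a covariate.** A reader might infer this from "The FDA has approved treatments for irritability in ASD, including aripiprazole and risperidone" in section B.III. That sentence concerns approvals in ASD. It says nothing about prognosis in PWS patients whose treatment must be stable (inclusion criterion 3).

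**Conclusion.** The point holds. Section G selects covariates by the wrong criterion and leaves the primary ABC-I model undetermined. The flag rate runs from 5% to 78% across plausible readings of one sentence, which itself shows how little is fixed.

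The power loss is conditional: about 3 to 16 points from 87% with 8 to 12 non-prognostic candidates, baseline correlation 0.5 and cut-offs between SMD 0.25 and p < 0.05. It is smaller or absent with prognostic candidates. Type I error stays near 5% under mechanical use and reaches about 6% to 8% only if the better of two results is reported. The correlation, the number of candidates and the cut-offs are all assumptions. The change is worth making before unblinding, but the pilot, exploratory status keeps the point below the most serious level.

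**What to change.** In section G, for the primary ABC-I analysis:

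1. Delete the imbalance rule and the data-driven choice between t-test and ANCOVA.
2. Name one primary model: the ANCOVA already described there, with week-12 ABC-I as outcome and treatment and baseline ABC-I as terms, fitted whatever the observed balance.
3. Allow at most one or two further covariates, chosen for expected prognostic value from data already collected, with the reason stated, and named before unblinding.
4. Keep the baseline table descriptive.
5. Report any imbalance-driven adjustment only as a labelled sensitivity analysis.

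The cost is a wording change, with no new data. Each covariate uses one degree of freedom and costs about 1 to 2 points of power if it turns out not to be prognostic. This applies to baseline ABC-I too: 76.7% against 78.0% if its correlation with the outcome were zero.

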**VI. Visit 8 (week 14, Follow-up, remote):**

The follow-up visit will be conducted remotely. Clinician will assess for any interval changes and monitor for potential withdraw symptoms or adverse events. Patients will be assessed using clinical scales including the CY-BOCS, HQ-CT, CGI-I, CGI-S, MERS-R-PWS, and C-SSRS. If patient didn't complete ABC assessment prior to the scheduled visit, it will be collected via clinician administration to the same reporter to ensure timely completion.

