## C.10. Schedule of Events

Procedure	Time Needed	Completed By			Screening (Remote)	Baseline (On Site)	Wk 2 (Remote)	Wk 4 (Remote)	Wk 6 (Remote)	Wk 8 (Remote)	Wk 10 (Remote)	Wk 12 / Early Term (On Site)	Wk 14 F/U (Remote)
		Parent	Child	Clinician									
Informed Consent	60 min	X	X	X	X	X							
I/E Criteria	10 min	X		X	X	X							
Medical Hx/Demographic	30 min	X		X	X								
Physical/Neuro Exam	20 min		X	X		X						X	
Psychiatric Interview	30 min	X	X	X	X								
IQ test (SB-5, Abbreviated)	20 min	X	X	X		X							
ECG	20 min		X	X		X						X	
Randomization	0 min					X							
Review Concomitant Medications	5 min	X		X	X	X	X	X	X	X	X	X	X
Drug Test	5 min		X		X*	X							
Pregnancy Test (if applicable)	5 min		X		X*	X		X*				X	
Vital signs, Weight, BMI	15 min		X	X		X						X	
CBC with differential and basic metabolic panel	15 min		X		X*	X		X*				X	
Liver Function Enzymes	15 min		X		X*	X	X*	X*				X	
AED drug levels (if applicable)	15 min		X			X		X				X	
Adverse Event Monitoring	10 min	X		X			X	X	X	X	X	X	X
Menstrual Diary Review (if applicable)	5 min	X				X		X		X		X	
Dispense Medication	5 min	X		X		X		X		X			

Scales	ABC-I	15 min	X			X	X		X		X		X	X
	RBS-R	20 min	X				X		X		X		X	
	CSQ	15 min	X				X		X		X		X	
	CY-BOCS	20 min	X		X		X		X		X		X	X
	HQ-CTx	15 min	X		X		X		X		X		X	X
	MERS-R-PWS	15 min	X		X		X		X		X		X	X
	CGI-I	5 min		X	X				X		X		X	X
	CGI-S	5 min		X	X	X	X		X		X		X	X
	C-SSRS	15 min	X	X	X		X	X	X	X	X	X	X	X
	Dietary Diary	15 mins	X				X		X		X		X	
	Actigraphy **	ongoing	X	X	X		X						X	

\*Denotes visit require outpatient Quest visit

\*\*Actigraphy device will be dispensed to participants after successful screening and prior to baseline visit, will collect minimum of 3 days of baseline data prior to randomization. Information collected continuously and reviewed at in person visit

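### The longitudinal model is written without within-patient correlation but credited with a mixed model's properties, and its visit window does not exclude the off-drug week-14 score

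*Combined protocol and SAP*

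**What the plan says.** Section G describes three kinds of comparison.

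- Group differences at a given time point, such as week 12, "will be compared with the two sample t-test or Wilcoxon rank sum test".
- A second comparison looks at change scores: "the change in outcome measures between baseline and 12 weeks will be compared between treatment groups", by t-test, or by ANCOVA if change depends on baseline.
- For longitudinal trends, "linear fixed effects models will be fit to all repeated measures obtained during follow-up, with main effects for time and treatment group". The model also has an interaction of the two, and the plan describes the approach as common in psychiatric research.

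No random effect, residual covariance, degrees-of-freedom method or list of visits is given, and the coding of time (continuous or categorical) is not stated. The next paragraph of section G, on loss to follow-up, says "The advantage of the mixed modeling approach is that it can handle data which are missing at random" and also unevenly spaced measurement times. No other longitudinal model appears in the plan, so this must refer to the same one.

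On the visit window, section C.3.3 sets 12 weeks of treatment. Section C.9.2 (VI) describes a remote week-14 visit titled Follow-up, where "Clinician will assess for any interval changes and monitor for potential withdraw symptoms or adverse events". That section provides for the ABC to be obtained at this visit, and the schedule in C.10 marks ABC-I there. Against this, section G opens by giving a 12-week follow-up, and section C.8.1 lists ABC-I at screening, baseline and weeks 4, 8 and 12 only. No sentence says whether the week-14 score enters the model.

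**The concern.** A model with only time, treatment and their interaction treats four or five scores from one patient as independent observations. Its standard errors are then wrong, and it lacks the missing-at-random property that the plan claims, because that property comes from a likelihood that models the within-patient covariance. If fixed effects meant one indicator per patient, the treatment main effect that the plan lists could not be estimated, since treatment does not vary within a patient. On either literal reading, the sentence does not give the analyst the model that the next paragraph relies on.

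The visit window is a separate matter. If all follow-up measures include week 14 and time enters as a straight line, the treatment-by-time slope mixes the effect on drug with whatever happens after dosing stops.

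This is also the only approach that the plan credits with handling missing data, in a trial that allows for 10% dropout. Leaving covariance, time coding and visits open allows choices after unblinding that could move the result in either direction.

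**Working it through.** **Inputs from the documents.** Section H: SD 8.27, treatment difference -8.26 in ABC-I change, 16 per group, two-sided 5%, 10% dropout. Visits: baseline and weeks 4, 8 and 12, plus week 14.

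**Assumptions not in the documents.** Within-patient correlation of 0.3, 0.5 or 0.7, either exchangeable or AR(1) per 4 weeks; an effect that grows linearly to -8.26 at week 12; 0%, 50% or 100% of it lost by week 14; complete data. The SD of the 0-to-12-week change is held at 8.27.

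**Step 1: the plan's own figure.** n per group = 2(1.96 + 0.842)² × (8.27/8.26)² = 15.7, so 16. Power at 16 per group is 80.6% by normal approximation and 78.0% by noncentral t. 32/0.9 = 35.6, so 36. The stated sample size reproduces.

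**Step 2: standard errors if independence is assumed.** For weeks 0, 4, 8 and 12, the squared deviations of time sum to 36 + 4 + 4 + 36 = 80. Worked case, exchangeable correlation 0.5:

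- Variance of one score: 8.27²/[2(1 - 0.5)] = 68.39.
- True SE of interaction × 12: √[(2/16) × 68.39 × 0.5 × 144/80] = 2.77.
- Expected residual variance with independent errors (124 df): 67.3. Reported SE: √[(2/16) × 67.3 × 144/80] = 3.89. Ratio 1.40.
- Size: 2Φ(-1.979 × 1.40) = 0.6%.
- Visit-averaged group difference. True SE: √[(2/16) × 68.39 × (1 + 3 × 0.5)/4] = 2.31. Reported SE: √[(2/16) × 67.3/4] = 1.45. Ratio 0.63, size 21%.

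The same calculation over the assumed range:

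| Structure, correlation | Interaction: reported/true SE | Size | Averaged difference: reported/true SE | Size |
|---|---|---|---|---|
| Exchangeable 0.3 | 1.19 | 1.9% | 0.72 | 15% |
| Exchangeable 0.5 | 1.40 | 0.6% | 0.63 | 21% |
| Exchangeable 0.7 | 1.81 | 0.04% | 0.56 | 27% |
| AR(1) 0.3 | 0.96 | 5.7% | 0.80 | 11% |
| AR(1) 0.5 | 1.00 | 4.8% | 0.69 | 17% |
| AR(1) 0.7 | 1.14 | 2.4% | 0.60 | 23% |

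**Step 3: week 14 with linear time.** Times 0, 4, 8, 12 and 14 have mean 7.6 and squared deviations summing to 131.2. The true differences are 0, 2.75, 5.51, 8.26 and d, where d is the difference left at week 14 (magnitudes shown).

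- Slope = (-3.6 × 2.753 + 0.4 × 5.507 + 4.4 × 8.26 + 6.4d)/131.2 = (28.63 + 6.4d)/131.2.
- Fitted week-12 difference = (16.52 + d)/5 + 4.4 × slope.

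| Effect lost by week 14 | d | Slope × 12 | Fitted week-12 difference |
|---|---|---|---|
| 0% | 8.26 | 7.45 | 7.69 |
| 50% | 4.13 | 5.04 | 5.98 |
| 100% | 0 | 2.62 | 4.26 |

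Even with no loss there is some dilution, because the assumed effect stops growing at week 12 while the line continues. A correctly correlated model with linear time gives the same three fitted differences under exchangeable correlation, and 7.45, 5.03 and 2.60 under AR(1) at 0.5. With categorical visits and complete data, the week-12 contrast stays at 8.26 whether or not week 14 is included.

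**The case against.** The strongest reply is that fixed is a slip for mixed. The next paragraph names mixed modelling outright, and the plan calls its approach widely used in longitudinal psychiatric research. A reader might infer from the wording that the trial will ignore within-patient correlation. The documents do not support that as a settled intention. What stands is a contradiction, and even after the word is corrected no random effect or covariance is specified.

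A reader might also infer that time is linear and that week 14 will be included. Neither is stated. Linear qualifies the model rather than time, although an interest in trends and in uneven spacing fits continuous time. The stated 12-week follow-up and the ABC-I timings in C.8.1 lean against week 14. Its inclusion is possible, not planned, and the assumed losses of effect have no source in the documents.

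Nor do the standard errors err in one direction. The interaction test is strongly conservative under exchangeable correlation but close to nominal under AR(1) at 0.3 and 0.5. The 11% to 27% error rates belong to a visit-averaged difference, which the plan does not name as its target.

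Finally, the week-12 t-test or Wilcoxon, the change and ANCOVA analyses, and the sample size do not depend on this model. That stands and limits the severity, although section G does not clearly rank its ABC-I analyses.

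**Conclusion.** The concern holds as a contradiction within section G together with an incomplete specification: a model with no within-patient correlation is described, and the missing-data property of a mixed model is claimed for it. Followed literally, it gives an interaction test whose true size is about 2% down to below 0.1% (exchangeable) or about 6% to 2% (AR(1)), and about 11% to 27% type I error for a visit-averaged difference. These figures rest on an assumed correlation of 0.3 to 0.7.

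The week-14 issue is conditional. If that visit is included and time is continuous, the fitted week-12 difference falls from 8.26 to about 7.7, 6.0 or 4.3 points for the assumed losses. Adding random effects while keeping linear time would not cure it.

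It would be too strong to say that the trial's main comparison is invalid. The separate week-12 and change analyses remain usable, and the plan describes the study as a pilot and exploratory. This is a moderate issue in a supporting analysis, to be settled before unblinding, and not a must-fix.

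**What to change.** Replace the longitudinal sentence in section G, so that it agrees with the missing-data paragraph, with a mixed model for repeated measures:

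- outcome: ABC-I at weeks 4, 8 and 12;
- fixed effects: treatment, categorical visit, treatment × visit and baseline score;
- a named within-patient covariance, for example unstructured (six parameters for three visits), with a stated fallback if it does not converge;
- a small-sample degrees-of-freedom method such as Kenward-Roger;
- the week-12 treatment contrast as the reported estimate.

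State that week 14 is excluded from efficacy models and summarised separately as off-treatment data. Apply the same rule to the other scales collected at week 14 (CY-BOCS, HQ-CT, MERS-R-PWS, CGI-I and CGI-S).

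A smaller edit (write mixed, name a covariance, state the coding of time and list the visits) would remove the contradiction. The fuller version is preferable because it gives an estimate at the time point on which the endpoint and sample size are based, and does not depend on a straight-line effect. The cost is analysis-plan wording: standard software, no new data and no change to visits or sample size.
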